	
Secondary Efficacy Endpoints
 
 • Time to first intubation/cannulation and bolus surfactant instillation between study treatments for first 7 days of life • Compare the proportion of infants across groups receiving multiple doses of surfactant. • Number of days on mechanical ventilation from the day of birth to 40 weeks PMA or discharge. • Number of days on supplemental oxygen administration from the day of birth to 40 weeks PMA or discharge • Survival without bronchopulmonary dysplasia (BPD) at 36 and 40 week PMA. (If an infant is discharged from the NICU prior to 36 and/or 40 weeks, a study member will call the family to verify the respiratory support status.) 
Safety and Tolerability Assessments
 
Safety and tolerability will be assessed through the monitoring of oxygenation, bradycardia, nasal congestion/aspiration, and other adverse events of interest (AEs) to 40 weeks PMA or discharge. Incidence of comorbidities of prematurity/AE's will be assessed. Tolerance of the AeroFact dosing administration and all doses of bolus surfactant will be assessed during and up to 24 hours following dosing.
 
Part II:
 
Additional Efficacy Endpoints
 
 • Assessment of pulmonary outcomes at 3, 6, 9 and 12 months corrected age • Length of NICU Stay (LOS) • Proportion of subjects with any respiratory resource utilization at 3, 6, 9 and 12 months corrected age • Respiratory morbidity per quarter till 12 months of corrected age • Assessment of modified GMFS (early neurologic) at 12 months of corrected age
Criteria for Individual Patient Discontinuation	
Aerogen Pharma, the Investigator or parent (s) may discontinue pre-term infants from the study at any time for the following reasons:
 
 • Safety • Withdrawal of parental consent • At the discretion of the Investigator

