Efficacy Analyses	
The primary analyses of the primary, secondary, and additional efficacy endpoints will be conducted on the ITT population. The PP population analyses of primary, secondary, and additional endpoints will be considered supportive.
 
For the efficacy endpoints the data will be summarized and compared according to the variable type:
 
 Continuous data summaries will include: 
 Descriptive summary of number of observations, mean, standard deviation, median, and minimum and maximum values. Analysis of Covariance (ANCOVA) or Mixed Model Repeated Measures (MMRM) adjusted for stratification factors for inferential statistics. Categorical data summaries will include: 
 Frequency counts and percentages Logit model or Generalized Estimating Equation (GEE) method adjusted for stratification factors and clustering of multiple births within a mother for inferential statistics Time-dependent data: Cox proportional hazards model will be used to analyze time dependent data and to depict the time to event data.
Safety Analyses	
Safety will be evaluated on the Safety Population.
 
The number and percent of infants experiencing TEAEs, serious adverse events, and TEAEs leading to study discontinuation will be summarized for each treatment group by Medical Dictionary for Regulatory Affairs (MedDRA) system organ class and/or preferred term. Additional summaries will include TEAE severity and relationship to study drug.

PK Sampling	Not applicable

Table 1 – Schedule of Assessments and Procedures – Part I and Part II

Part I								Part II
		Day 1	Day 2-4	Day 5 – Day 28	36 Weeks PMA	40 Wks PMA	Discharge	3, 6, 9, 12 Months Corrected Age
Informed Consent ¹	X							
Demographics		X						
Maternal/Infant Medical History		X						
Chest Radiograph or Lung Ultrasound		X						
Medication History		X						
Inclusion/Exclusion Criteria		X						
Randomization		X						
Clinical Blood Gas Assessments ²		X	X					
Weight, Recumbent Length, Head Circumference ³		X					X	X
Administer AeroFact or begin nCPAP/nIMV alone ⁴⁻⁵		X	X					
Oxygenation and Respiratory Parameters ⁶⁻⁷		X	X	X	X ⁸	X ⁸		
Nasal Congestion Assessment ⁹		X	X					
Dosing Tolerance ¹⁰		X	X					
AE/Co-Morbidities Monitoring		X	X	X	X		X	
Concomitant Medications		X	X	X	X		X	
Feeding Status/Pulmonary Questionnaire/Audiology/Ophthalmology Reports							X	
Room Air Challenge (RAC) ¹¹					X	X		

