10.1.2 Screening (Assessment for Eligibility)

Preterm infants will be assessed for eligibility on Day 1. The following items will be assessed:

- Chest radiograph or lung ultrasound
- Gestational age and demographics (including date of birth, gender, race, and ethnicity)
- Medical history for mother and infant (including current medications)
- Birth weight, Recumbent Length, and Head Circumference
- Apgar Scores
- Respiratory support parameters (FiO₂, SpO₂, PEEP/CPAP pressure and flow rate, Paw, and Respiratory Support Status) (initial stabilization in delivery room, first stabilization in NICU, and one hour post nCPAP start)
- Qualifying RSS based on FiO₂ and CPAP calculated from parameters above
- Inclusion and exclusion criteria

The following items will be obtained prior to dosing:

- If a blood gas has been obtained for clinical purposes only, record PO₂, PCO₂, pH, bicarbonate prior to randomization/dosing, and/or as verification for meeting intubation criteria or in relationship to an SAE.
- Assess and document nasal congestion just prior to AeroFact dosing
- Evaluate identified Co-Morbidities of Prematurity prior to AeroFact dosing

If the baby has been assessed as eligible to participate in study and informed consent has been obtained, the baby may be enrolled into the study.

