12.3 Sample Size Determination and Rationale

[figure not shown]
Two hundred and sixty-one (261) subjects (87 in each arm) will be randomized in a 1:1:1 ratio in order to assure that 246 subjects (82 in each arm) complete the study. The randomization will be stratified by site, gestational age and dosing group.

Infants requiring treatment escalation in the AeroFact dose groups is estimated to be 20% and in the control group is estimated to be 40%, with an odds ratio of 0.375.

Under the above assumptions, 82 subjects in each treatment group will be required, to meet the Type I error rate of 0.05 and 80% statistical power. To accommodate the potential dropouts, a 5% dropout rate is included in this sample size calculation.

The sample size is depicted in Figure 12.1.

Figure 12-1: Sample Size

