12.12 Statistical Methods

A Statistical Analysis Plan (SAP) will be developed and approved before the database is locked. The SAP will present the detailed statistical methodology to be used in analyzing the efficacy and safety data from this trial. All inferential statistical analysis will be based on a two-sided test with a Type I error rate of 0.05.

All the efficacy analyses presented here will be conducted using both ITT and PP populations. All safety analyses will be conducted using the Safety population. All data collected will be summarized according to the variable type.

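### The stated model for continuous endpoints adjusts for gestational age only through a two-level stratum; adding it in days would recover some precision for length of stay, and perhaps for oxygen and ventilation days, at almost no cost.

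*Combined protocol and SAP*

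**What the plan says.** The Efficacy Analyses row of the synopsis and Section 12.13 give the same inferential method for continuous data: "Analysis of Covariance (ANCOVA) or Mixed Model Repeated Measures (MMRM) adjusted for stratification factors for inferential statistics". Sections 12.4 and 12.5 name the stratification factors as site and gestational age, cut into 26 0/7 to 28 6/7 weeks and 29 0/7 to 31 6/7 weeks. Section 12.10 leaves covariates to the SAP and names none. No SAP text is among the documents supplied.

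Three duration endpoints are relevant. Two are secondary (synopsis and Section 7.2): days on mechanical ventilation, and "Number of days on supplemental oxygen administration from the day of birth to 40 weeks PMA or discharge". The third, length of NICU stay, is an additional endpoint (Section 7.3). It has no definition, no stopping point, no SD and no target effect.

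Gestational age is needed for eligibility (Section 5.1) and is recorded at screening (Section 10.1.2).

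**The concern.** Two infants in the same stratum can differ by up to 20 days in gestational age, and the stated model treats them as alike. If a duration endpoint falls as gestational age rises, that known baseline difference stays in the error term, where it widens confidence intervals and lowers power.

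What is at stake is precision on secondary and additional endpoints. Ventilation and oxygen days also belong to the secondary family that Section 12.11 protects with a closed testing procedure, in an order still to be set in the SAP. A step missed for want of precision could stop the tests that follow it.

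**Working it through.** **Inputs from the protocol.** The eligible range is 26 0/7 to 31 6/7 weeks, or 182 to 223 days (Section 5.1). The strata are 182–202 and 203–223 days, 21 values each (Section 12.5). There are 82 infants per arm completing (Section 12.3: "in order to assure that 246 subjects (82 in each arm) complete the study"). Tests are two-sided at 0.05 (Section 12.12).

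**Assumptions, because the documents give no figure.** Gestational age is uniform over the eligible range. The endpoint has a linear slope of *b* days per day of gestational age. The residual SD is *s* days once gestational age in days is in the model. Infants are independent, so sibling clustering is ignored.

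**1. The plan's own figure.** For 40% against 20%, with pooled variance under the null and 80% power:

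n = [1.960·√(2·0.30·0.70) + 0.842·√(0.24 + 0.16)]² / 0.20² ≈ 81.2, so 82 per arm.

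82/0.95 = 86.3, so 87 per arm. The odds ratio is (0.20/0.80)/(0.40/0.60) = 0.375. All three reproduce. They concern the primary endpoint only. The documents contain no power calculation for a duration endpoint.

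**2. How much gestational-age variance the strata remove.**

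- Total variance over 42 days: (42² − 1)/12 = 146.9 (SD 12.1 days).
- Variance within a 21-day band: (21² − 1)/12 = 36.67 (SD 6.06 days).
- Share removed by the two bands: 1 − 36.67/146.9 = 75%.

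If enrolment is tilted 3:1 toward either end of the range, the within-band variance is 35.8 and the share removed is 73%.

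**3. What the remainder costs.** The error variance is b²·36.67 + s² with the strata alone, and s² with gestational age in days added. The proportional fall in the standard error is 1 − s/√(b²·36.67 + s²). For example, at b = 1 and s = 10 it is 1 − 10/√136.67 = 1 − 0.855 = 14%.

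The last two columns use 82 per arm. The detectable difference is (1.960 + 0.842)·SD·√(2/82), at 80% power.

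| Slope b | Residual SD s | Fall in SE | Power with strata alone, where adding days gives 80% | Detectable difference in days: strata alone / days added |
|---|---|---|---|---|
| 1 | 7 | 24% | 56% | 4.05 / 3.06 |
| 1 | 10 | 14% | 67% | 5.11 / 4.38 |
| 1 | 14 | 8% | 73% | 6.67 / 6.13 |
| 1 | 21 | 4% | 77% | 9.56 / 9.19 |
| 1 | 28 | 2% | 78% | 12.53 / 12.25 |
| 0.5 | 10 | 4% | 77% | 4.57 / 4.38 |
| 0.5 | 14 | 2% | 78% | 6.27 / 6.13 |

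At b = 1 and s = 10, 82 infants per arm analysed with the strata alone carry the information of about 82·100/136.67 = 60 analysed with gestational age in days.

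**4. Which endpoints the slope can apply to.** For oxygen and ventilation days the counting window closes at 40 weeks PMA (280 days) or discharge. The longest possible count is therefore 280 minus gestational age: 78 to 98 days in the lower stratum and 57 to 77 in the upper. That maximum falls day for day, but the documents do not show that the count itself does. For length of stay no such window is stated, and the slope is a plausible assumption only.

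**The case against.** The strongest reply is that the protocol gives a summary and leaves covariates to the SAP, so gestational age in days may yet be specified. Methods are also assigned by variable type, and no text says that length of stay or oxygen days will be analysed by ANCOVA. This stands as a limit on how firmly the point can be put. It does not dispose of it, because the only continuous-data model in writing contains the strata alone and Section 12.10 names nothing that fills the gap.

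A second reply is that the loss may be trivial. That is correct at a residual SD of 21 days or more, or at half the slope with SD 10 or more. The two bands already do most of the work. Adjusting for the stratification factors is a valid analysis, and none of these endpoints is powered.

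Three stronger readings are tempting, and the documents do not support them:

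- **That length of stay is capped at 40 weeks PMA.** That window is attached to ventilation and oxygen days only. The Appendix II questionnaire allows for infants who are still in-patients at the corrected-age interviews.
- **That oxygen days fall almost day for day with gestational age.** The window limits the count but does not set it. Entry requires an RSS of 1.4–2.0. At a pressure of 7 or 8 cm H₂O in room air the RSS is 7 × 0.21 = 1.47 or 8 × 0.21 = 1.68, so an infant can qualify with no supplemental oxygen.
- **That chance imbalance in gestational age is a further harm.** The difference in mean gestational age left between two arms has a standard error of √(2·36.67/82) = 0.95 days. Multiplied by the slope, this is the same noise already counted in the wider standard error. Under randomization it is not bias, and the confidence interval allows for it.

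**Conclusion.** The point holds as a modest loss of efficiency. On the model as written, gestational age enters in two levels, and a within-band SD of about 6 days is left unexplained. For length of stay, adding gestational age in days would cut the standard error by 24% to 8% if the slope is 1 and the residual SD is 7 to 14 days. The cut is about 4% or less if the residual SD is 21 days or more, or if the slope is 0.5 with SD 10 or more. The slope, the residual SD and uniform enrolment are all assumptions. For oxygen and ventilation days the gain could be small and cannot be sized from the documents. Neither the validity of the comparisons nor the primary endpoint and its sample size is affected. The priority is low to moderate, and the change is worth making because it is nearly free.

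**What to change.** In Section 12.13, the Efficacy Analyses row of the synopsis and the SAP, state that the models for length of NICU stay, oxygen days and ventilation days include gestational age at birth in days as a continuous covariate, in addition to the randomization strata. If a rank-based or ordinal model is chosen for these counts, the covariate can be carried into it. Fix the wording before outcome data are examined by arm.

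The cost is a line of text and one degree of freedom. Gestational age is already established for eligibility, so there is nothing new to collect. If the slope proves weak, the loss of precision is negligible.

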13.2.8	Handling of Study Investigational Product	57
13.2.9	Publication of Results	57
13.2.10	Disclosure and Confidentiality	57
13.2.11	Discontinuation of Study	57
13.2.12	Patient Insurance and Indemnity	58
14	REFERENCES	59
15	APPENDIX I- PART I DISCHARGE BREATHING QUESTIONNAIRE	61
16	APPENDIX II – PART II QUESTIONNAIRE.....	63

LIST OF ACRONYMS, ABBREVIATIONS AND DEFINITION OF TERMS

Abbreviation	Term
AE	Adverse Event
AF	AeroFact
AGA	Appropriate for Gestational Age
APC	Aerogen Pharma Corporation
BiPAP	Bilevel Positive Airway Pressure
BP	Blood Pressure
BPD	Bronchopulmonary Dysplasia
CFR	Code of Federal Regulations
CLN	Clinical
CMV	Continuous Mandatory Ventilation
Corrected Age	Chronological Age - Weeks Premature
CPAP	Continuous Positive Airway Pressure
CRA	Clinical Research Associate
CRF	Case Report Form
CRO	Contract Research Organization
CSR	Clinical Study Report
CV	Coefficient of Variation
Cystic PVL	Cystic Periventricular Leukomalacia
DSMB	Data Safety Monitoring Board
ETT	Endotracheal Tube
FDA	Food and Drug Administration
FiO ₂	Fraction of Inspired Oxygen
GCP	Good Clinical Practice
GMFS	Gross Motor Function Score (Modified)
HFJV	High Frequency Jet Ventilation
HFNC	High Flow Nasal Cannula
HFOV	High Frequency Oscillatory Ventilation
HR	Heart Rate
IB	Investigator's Brochure
ICF	Informed Consent Form
ICH	International Conference on Harmonization
IEC	Independent Ethics Committee
ITT	Intention to Treat
IRB	Institutional Review Board
IVH	Intraventricular Hemorrhage
IP	Investigational Product
kg	Kilogram
LOS	Length of Stay
MAP	Mean airway pressure

Abbreviation	Term
MedDRA	Medical Dictionary for Regulatory Activities
mg	milligram
min	Minute
MOP	Manual of Procedures
NC	Nasal Cannula
nCPAP	Nasal Continuous Positive Airway Pressure
NEC	Necrotizing Enterocolitis
NICU	Neonatal Intensive Care Unit
NIH	National Institutes of Health
nIMV	Nasal Intermittent Mandatory Ventilation
O ₂	Oxygen
OTC	Over-the-Counter
PCO ₂	Partial Pressure of Carbon Dioxide
PO ₂	Partial Pressure of Oxygen
Paw	Mean Airway Pressure
PDA	Patent Ductus Arteriosus
PEEP	Positive-End Expiratory Pressure
PHT	Pulmonary Hypertension
PIE	Pulmonary Interstitial Emphysema
PIP	Peak Inspiratory Pressure
PMA	Postmenstrual Age
PPP	Per Protocol Population
PPHN	Persistent Pulmonary Hypertension in the Neonate
PROM	Premature Rupture of Membranes
RAC	Room Air Challenge
RDS	Respiratory Distress Syndrome
Respiration Sensor	aka Breath Sensor
ROP	Retinopathy of Prematurity
RR	Respiration Rate
RSS	Respiratory Severity Score = CPAP or MAP (cm H ₂ O) x FiO ₂
SAE	Serious Adverse Event
SE	Standard Error
SOP	Standard Operating Procedures
SpO ₂	Oxygen Saturation
TEAE	Treatment-Emergent Adverse Event
TLD	Target Lung Dose
T ₀	Start of AeroFact dose
WHO	World Health Organization

2 BACKGROUND AND RATIONALE

2.1 Introduction

Aerogen Pharma is developing AeroFact, an investigational drug/device combination product consisting of lyophilized bovine-origin surfactant SF-RI 1 (sold in Europe since 1989 under the proprietary name AlveoFact®) administered following reconstitution to a 45 mg/ml suspension with semi-isotonic saline buffer using a proprietary breath-actuated vibrating mesh nebulizer with a nasal cannula interface.

Current surfactants used for prevention or treatment of Respiratory Distress Syndrome (RDS) in preterm infants are approved for delivery only as a liquid bolus instillation via an endotracheal tube (ETT) while intubated/cannulated. Intubation and cannulation with a tube into the trachea for surfactant administration are associated with adverse events (AEs) [1,2,3]. Access to surfactant therapy without invasive procedures that further exacerbate the condition is therefore a major unmet medical need in this vulnerable population. Reports suggest that AEs caused by intubation or cannulation can be avoided if there is a means of non-invasive delivery, i.e. aerosolized surfactant delivered through nasal continuous positive airway pressure (nCPAP) [5].

Current therapies for RDS in preterm infants are associated with the following challenges:

- Endotracheal intubation of preterm infants is an invasive procedure associated with airway tissue trauma, vagal stimulation, hypoxia, and bradycardia [1,2,3]. Additionally, insertion of small catheters into the infant trachea and positioning above the bifurcation can be traumatic. Both techniques require specialized skills, medical support, and training that must be kept current via frequent practice.
- Liquid bolus surfactant instillation via ETT is associated with airway obstruction (due to the large volume of liquid relative to preterm infant lung volumes) and transient physiological events such as hypoventilation, hyperventilation, changes in systemic blood pressure, alterations of cerebral blood flow, and other pulmonary and neurological effects.
- Respiratory support with nCPAP alone, albeit less traumatic compared to intubation/mechanical ventilation, results in delayed delivery of surfactant or absence of exogenous surfactant administration. This can lead to:
 - Atelectasis
 - Stress within the lungs associated with pneumothoraces and bronchopulmonary dysplasia (BPD)
 - Increased fraction of inspired oxygen (FiO₂) requirements, which are associated with lung toxicity and ophthalmic vascular changes leading to Retinopathy of Prematurity (ROP)
 - Ventilation/perfusion mismatching resulting in intra-pulmonary and intra-cardiac shunts

In summary, as practice has evolved, many clinicians avoid subjecting preterm infants to risk of intubation/cannulation and instillation of liquid bolus surfactant until RDS has progressed to moderate or severe levels.

2.2 AeroFact

2.2.1 Nonclinical Experience

SF-RI 1 (the drug component of AeroFact) delivered as a bolus instillation has been assessed in a series of nonclinical studies in order to gain regulatory approval in several European countries and territories around the world. (Please refer to the Investigator's Brochure on non-clinical trials conducted with Alveofact). These nonclinical studies have been deemed acceptable to support the safety of SF-RI 1 for intratracheal bolus instillation in preterm neonates.

Several studies comparing IT instillation of surfactant to nebulized surfactant indicate potential advantages to inhaled aerosol therapy. Efficacy has been demonstrated by the Sponsor, using aerosolized SF-RI 1. In these studies, using a breath synchronized vibrating mesh nebulizer, similar to the clinical delivery platform, rabbits with surfactant depleted lungs from repeated saline washes, showed improvement in the oxygenation index and ventilation efficiency index after intratracheal delivery of aerosolized SF-RI 1. These data support the safe use of aerosolized SF-RI 1 in preventing progression of infant respiratory distress syndrome (RDS) when delivered either as a bolus instillation or as an aerosol.

Because SF-RI 1 administration with AeroFact is by a new route (nebulized aerosol passing through the neonate's nose to be delivered to the lungs), the potential toxicity of SF-RI 1 to the nasal cavity, and general lung tolerability, were evaluated by the Sponsor in support of the proposed clinical development program. Specifically, the toxicity and local tolerability of SF-RI 1 were assessed in two 14-day GLP studies, one in post-weanling Sprague Dawley rats and one in post-weanling New Zealand White rabbits. For these studies, nose only inhalation was used as this is the intended clinical route. Additionally, the drug was administered daily for 14 consecutive days, which exceeds the frequency of dosing in the clinical situation. The high dose in the 14-day animal studies was determined by using the maximum feasible concentration for SF-RI 1 in an attempt to obtain an acceptable margin over the anticipated clinical dose. In both studies standard parameters were assessed including, body weight, food consumption, clinical observations, clinical pathology (hematology, coagulation and clinical chemistry) and ophthalmology, as well as a complete necropsy and histopathology of over 50 tissues. No adverse effects were observed in any standard assessment of toxicity, including the electrocardiogram. Technical issues with the rabbit study resulted in lower-than-targeted aerosol exposure. Inflammation and increased alveolar macrophages were present in all treatment groups including the control. Therefore, a No-Observed-Adverse-Effect-Level (NOAEL) was not determined. In rats, based on the absence of any adverse findings in any of the measured parameters, the NOAEL from 14 days of nose-only inhalation of SF-RI 1 was considered to be the maximal feasible dose of 1,223 mg/kg/day.

2.2.2 Clinical Experience

More detailed summaries of AeroFact clinical experience can be found in the Investigator Brochure.

APC-AF-CLN-001, a Phase 2a study of AeroFact, was performed in three clinical centers in Australia. Only two of the centers enrolled subjects. The third site withdrew from the study prior to enrolling any subjects. The enrollment period was 21 November 2017 to 1 August 2018. The study was An Open-Label Study of the Safety and Tolerability of AeroFactTM (Aerosolized Alveofact[®]) in Preterm Infants on nCPAP at Risk of Worsening Respiratory Distress Syndrome.

The study was conducted in 2 parts, Part I, single dose and Part II, multiple dose. Each part was conducted in a separate group of preterm infants.

Infants who were 26 0/7 to 30 6/7 weeks gestational age at birth, required CPAP or nIMV after the delivery room, and satisfied the inclusion and exclusion criteria were enrolled within two hours into this study. For each enrolled infant, retrospective data was collected on 3 comparative infants of the same gestational age who were born within the two previous years.

AeroFact treatment failure criteria for intubation and bolus instillation of surfactant were one or more of the following:

